Our goals in this study are:

- 1. To evaluate the effectiveness of surgical decompression in migraine headaches prospectively, using validated instruments, and to compare it to the effectiveness of a botulinum toxin injection protocol
 - a. Our hypothesis is that migraine surgery decreases the frequency and severity of migraine headaches significantly, as measured by

validated questionnaires, and that the reduction is greater and more sustainable than that seen with a botulinum toxin injection protocol

- 2. To determine which types of migraine headaches benefit most from surgical decompression and/or botulinum toxin injection
- 3. To identify prognostic factors for the success or failure of surgical decompression in migraine headache
 - a. These have been demonstrated in a previous study,⁹ but have not evaluated in a multi-center fashion.
- 4. To compare the long-term direct and indirect costs in patients with migraine headaches undergoing botulinum toxin A injections versus surgical decompression
 - a. We hypothesize that, over the long-term, surgical decompression is more cost-efficient than a botulinum toxin injection protocol

III. Procedures

a. Research design

This is a **prospective, multi-center** evaluation of the short, medium and long-term efficacy of surgical decompression in migraine headaches, comparing it to the efficacy of a botulinum toxin injection protocol.

b. Sample

Inclusion criteria:

-Patients with migraines related to a trigger site at the location of a branch of a cranial nerve (frontal, temporal, occipital)

-Patients with chronic migraine (≥15 days per month) as dictated by the FDA indication for botulinum, and as diagnosed by a board-certified neurologist

Exclusion criteria:

-Patients deemed by the senior author or the neurologist to not have migraine headaches, but an alternative diagnosis

-Patients with systemic conditions that make them poor candidates for surgery (coronary artery disease, uncontrolled diabetes mellitus, etc...)

-Patients with migraines related to inferior turbinate hypertrophy or septal deviation -Patients with a frontal, temporal or occipital trigger point who do not respond to a diagnostic botulinum toxin injection

-Hypersensitivity to any botulinum toxin preparation or to any of the components in the formulation

-Infection at the proposed injection site for botulinum

Sample size (power analysis)

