Since there are several endpoints in this study, the required sample size can be calculated in several ways:

-Using efficacy as an endpoint:

In Janis *et al*,⁶ patients undergoing botulinum toxin injections had an average improvement in their Migraine Headache Index of 87.5%. In comparison, patients undergoing surgery had an average improvement of 96.6%.

Assuming a standard deviation of 20%, an alpha error of 5%, and a power of 80%, the required sample size using this method is **30 patients in each group**.

-Using total cost of treatment as an endpoint:

Assuming an average injection volume of 75 Units of botulinum toxin every 3 months, and assuming a cost of \$12-15 per Unit, the estimated cost of a botulinum toxin A injection protocol over one year is \$3,600-\$4,500.

In comparison, the estimated cost of surgery (including facility fee, surgeon fee, preoperative testing and follow-up) is \$8,378.¹⁰

Therefore, in order to demonstrate a financial superiority of surgery versus botulinum toxin, the patients would need to be follow-up for 1.9 to 2.3 years. Assuming a study follow-up of 2.5 years, and average costs of botulinum and surgery of $$10,125 \pm $2,000$ and $$8,378 \pm $2,000$, respectively, and assuming an alpha error of 5%, a power of 80%, the required sample size using this method is **16 patients in each group**.

-Using treatment success by trigger site as an endpoint:

According to Larson *et al*,⁹ the success rates for surgery by trigger site were as follows: Frontal 83.3%, temporal 75.8%, and occipital 45.5%. In order to discern a difference between the outcomes for the two sites with the closest outcomes (frontal and temporal), and assuming a standard deviation of 10%, an alpha error of 5%, and a power of 80%, the required sample size using this method is **14 patients in each group**.

Looking at the three methods above, keeping the method yielding the highest required number of participants, and accounting for any participant drop-out, we will seek to enroll **50 patients in each group.**

c. Detailed study procedures

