Prospective, Multi-Center Evaluation of the Efficacy of Migraine Surgery

Statistical Analysis Plan

IRB Approval #:2015H0024

NCT02351544

Document Date Version: February 16, 2014

Principal Investigator: [name], FACS (The Ohio State University)

Outcomes

**Outcomes modeled were: MHI, MIDAS A, MIDAS B, MIDAS Total, MSQ Sum and MWPLQ7 Total

Data Analysis

Descriptive statistics, such as frequency and percents, were displayed for sex (male or female), treatment (Botox or Surgery) and site (OSU or MGH). Descriptive statistics, such as mean, standard deviation, median, lower quartile and upper quartile, were reported for age and the patient reported outcomes with the respect to their migraine for each time point (baseline, 1 year, 2 years and 2.5 years).

Each of six outcomes were highly skewed and therefore natural logarithm was applied to each one before it was modeled. A constant of 1 was added to outcome values before applying natural log function so as to include raw values of zeros.

Linear mixed models with a random effect for patient were used to evaluate the changes in each of six outcomes between two different treatments over time with inclusion of interaction between treatment and time. These models were used given to account for correlation between repeated measurements on the same patient and to account for missing data across time points. P-values for both the main and interaction effects of time and treatment were reported for each model and Tukey's post hoc method was used to adjust for pairwise comparisons. For the ease of interpretation, raw means and SDs are presented for each time point within specific treatment.

Analyses were performed using SAS v9.4 (SAS Institute; Cary, NC; www.sas.com). Statistical significance was defined as two-sided alpha<0.05.

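### The SAP's patient random effect, read as written, fixes one variance and one correlation across all four visits; this can misstate the standard errors of change contrasts, by an amount and in a direction the documents do not settle.

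*SAP*

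**What the plan says.** The SAP (Data Analysis) says: "Linear mixed models with a random effect for patient were used to evaluate the changes in each of six outcomes", with a treatment-by-time interaction. Its stated reason is "to account for correlation between repeated measurements on the same patient and to account for missing data across time points". Outcomes are summarised "for each time point (baseline, 1 year, 2 years and 2.5 years"), and the model is fitted after a log transform: "A constant of 1 was added to outcome values before applying natural log function so as to include raw values of zeros".

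On testing it says "P-values for both the main and interaction effects of time and treatment were reported for each model and Tukey's post hoc method was used", the last of these being the multiplicity correction for pairs. The threshold is given as "Statistical significance was defined as two-sided alpha<0.05". It names no residual covariance structure, visit-specific variance, robust standard error or degrees-of-freedom method.

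The Protocol (III.b, Inclusion criteria) admits "Patients with chronic migraine (≥15 days per month"). Its sample size section says "we will seek to enroll 50 patients in each group".

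**The concern.** A random intercept with independent residuals gives every visit the same variance and every pair of visits the same correlation. Three features of the design make that doubtful:

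- Baseline precedes treatment and all three follow-ups come after it. If some patients respond and others do not, follow-ups may agree with each other more than with baseline.
- Entry requires a minimum headache frequency, so headache frequency may be less spread at baseline than later. The documents record no such restriction for the MSQ or MWPLQ outcomes.
- The visits are 1, 1 and 0.5 years apart.

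If the true covariance differs, the model uses one averaged variance for all within-patient differences. Contrasts of baseline with follow-up, and of one follow-up with another, then get the wrong standard errors, often in opposite directions. The first kind shows whether change differs by treatment. The second bears on the Protocol's hypothesis (Objectives, 1a) that surgery's benefit lasts longer. The SAP also relies on this model for missing visits, and likelihood-based handling of missing data depends on a correctly specified covariance.

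**Working it through.** **Inputs from the documents.** Four visits; 50 patients per group; two-sided 0.05; a patient random effect as the only covariance term.

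**Assumed inputs.** Correlation of baseline with follow-up 0.3-0.4; correlation among follow-ups 0.6-0.8; log-scale SD either equal at all visits, or 0.5 at baseline and 1.5 at each follow-up. Correlation pairs below are written baseline/follow-up, then among follow-ups.

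**Formula.** For visits j and k, the true variance of a within-patient difference is D = σj² + σk² − 2ρσjσk. With complete data, the random-intercept model replaces each D by P, the mean of the six pairwise values. Let D0 be the baseline-to-follow-up value and DF the follow-up-to-follow-up value. When all follow-ups behave alike, three pairs are of each kind, so P = (D0 + DF)/2. Then:

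- type I error of the single-visit change contrast = 2[1 − Φ(1.96/√(D0/P))]
- ratio of model to true standard error between follow-ups = √(P/DF)

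Group size cancels.

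**Control: the nominal 5%.** Equal SD, all correlations 0.5: D0 = DF = P = 1, ratio 1, type I error 5.0% (simulated 5.1%).

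**Across the assumed range.**

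| SD baseline, later | Correlations | D0 | DF | P | D0/P | Type I error | Follow-up SE ratio |
|---|---|---|---|---|---|---|---|
| equal (1) | 0.4/0.6 | 1.2 | 0.8 | 1.0 | 1.20 | 7.4% | 1.12 |
| equal (1) | 0.3/0.7 | 1.4 | 0.6 | 1.0 | 1.40 | 9.8% | 1.29 |
| equal (1) | 0.3/0.8 | 1.4 | 0.4 | 0.9 | 1.56 | 11.6% | 1.50 |
| 0.5, 1.5 | 0.4/0.6 | 1.9 | 1.8 | 1.85 | 1.03 | 5.3% | 1.01 |
| 0.5, 1.5 | 0.4/0.8 | 1.9 | 0.9 | 1.4 | 1.36 | 9.2% | 1.25 |

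As a worked case, for SD 0.5 and 1.5 at 0.4/0.6: D0 = 0.25 + 2.25 − 2(0.4)(0.75) = 1.9 and DF = 4.5 − 2(0.6)(2.25) = 1.8.

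Simulation (50 per arm, 20,000 trials, complete data) gives 7.5% at 0.4/0.6 and 9.6% at 0.3/0.7 with equal SDs. Giving the contrast its own variance, as an unstructured covariance does with complete data, returns about 5%.

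**Unequal variance alone.** SD 0.5 then 1.5, all correlations 0.5: D0 = 0.25 + 2.25 − 0.75 = 1.75; DF = 4.5 − 2.25 = 2.25; P = 2.0; D0/P = 0.875. Type I error is 3.6% (simulated about 3.5%), which is conservative. The follow-up standard error is now too small: √(2.0/2.25) = 0.94.

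**Correlation that decays with time.** At 0.7 per year and equal SDs, the contrast's type I error is 2.7% at 1 year, 9.1% at 2 years and 11.6% at 2.5 years. The direction can therefore differ by visit.

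**The tests the SAP names.** The simulated 3-df treatment-by-time test, equal SDs, is about 5.2-5.5% at 0.4/0.6 and 6.5% at 0.3/0.7; with SD 0.5 then 1.5 at 0.4/0.8 it is 5.9%. For a Tukey-adjusted baseline-to-follow-up comparison within an arm (assuming all 8 treatment-by-visit cells, critical value 3.05), per-comparison error rises from 0.0023 to 0.0099 when D0/P = 1.4.

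**Missing visits.** With assumed loss to 30 per arm by 2.5 years (the Protocol gives no rate) and 0.3/0.7, the change contrast runs at 9.0%, 9.2% and 8.3% at 1, 2 and 2.5 years.

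**The case against.** A reader might infer that the false-positive rate of the trial's treatment-by-time answer is roughly doubled. The documents do not support that. The near-doubling belongs to an unadjusted contrast of one follow-up with baseline. The SAP does not name that contrast; it names main effects, the interaction and Tukey-adjusted pairs. The interaction test stays at about 5-7% over the assumed range, and the adjusted pairs stay far below 5% each. This objection stands, and it limits the point.

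Three further objections also stand in part:

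- **Direction.** The features documented most clearly, the entry threshold and the allowance for zeros, concern unequal variance. Alone, in the case worked here, that makes the baseline contrast conservative. Inflation comes from correlations that appear nowhere in the documents. Nor are follow-ups uniformly closer in time: 1 to 2.5 years is a longer gap than baseline to 1 year. It cannot be said flatly that the standard error is too small.
- **Silence.** The SAP does not exclude a residual structure. If one was fitted, there is nothing to correct except the description.
- **Timing.** The SAP reports the analysis as done, so a change means refitting after results were seen.

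What survives is that the model as described carries a restrictive assumption that the SAP does not justify, and that four visits and about 100 patients do not require it.

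**Conclusion.** The point holds conditionally. As written, the model imposes equal variance and equal correlation on one pre-treatment and three post-treatment visits. Under the assumed correlations (0.3-0.4 with baseline, 0.6-0.8 among follow-ups, SDs equal or 0.5 then 1.5), the error of an unadjusted single-visit change contrast is about 5-12% and that of the named interaction test about 5-7%. Follow-up-to-follow-up standard errors are about 1-50% too large, which weakens the test of durability. With other plausible covariances the baseline contrast is conservative. The documents cannot settle which case applies, and they do not show that any named test approaches a doubling of 5%. This is an inexpensive improvement worth making; it does not show that the reported conclusions are wrong.

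**What to change.** State the covariance structure. Replace the random intercept with an unstructured within-patient covariance over the four visits (REPEATED with TYPE=UN in SAS) and Kenward-Roger degrees of freedom. Name heterogeneous Toeplitz as the fallback if the model does not converge, noting that it orders visits by position and not by elapsed time. The unstructured form has 4 variances and 6 covariances, 10 parameters in all, which about 100 patients can support.

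Because the SAP is in the past tense, refit all six outcome models, report both sets of results, and say whether any conclusion changes. If a residual structure was already fitted, one sentence naming it is enough.

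The cost is six refits and one SAP sentence, slightly fewer effective degrees of freedom, and possible non-convergence, which the fallback covers.

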A neurologist will evaluate patients presenting for evaluation for treatment of migraine headaches, for confirmation of the diagnosis of migraine. The type of migraine that they suffer from will be recorded. If the diagnosis of migraine is confirmed, they will sign an informed consent form, and they will be asked to complete a daily headache diary, and keep track of their 1) daily use of medications for migraines, 2) physician visits for migraines, 3) ER visits for migraines, 4) days of work lost due to migraines, 5) other costs directly related to migraines for 2 months. They will also be asked to

complete three questionnaires: the Migraine Work and Productivity Loss Questionnaire (MWPLQ),¹¹ the Migraine Disability Assessment questionnaire (MIDAS)¹² and the Migraine-Specific Quality of Life questionnaire (MSQ) at the time of enrollment.

All patients will undergo a history and physical examination, including an intranasal examination. This will include determination of the possible trigger site: frontal, temporal, occipital, and inferior turbinate/septum. The trigger site can be determined using a combination of three methods: 1) Physical examination, 2) Diagnostic botulinum toxin injection into a specific trigger point, and 3) Nerve block using a local anesthetic injected into a specific trigger point in patients having active symptoms.

The patients will be asked whether they prefer to undergo surgical decompression or a botulinum toxin protocol, and their preference will be recorded.

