and the Migraine-Specific Quality of Life questionnaire (MSQ). They will also be examined by a board-certified neurologist at 1 year postoperatively.

The Botox injections and the surgeries are being done as part of the routine clinical care for the patients enrolled in the study. The only procedures being done solely for research purposes are having the patients fill out the surveys and diaries.

d. Measurements

The measurements will include

- 1) Number of migraine headaches per 30 days
- 2) Cost of migraine-related medications, physician visits, ER visits
- 3) Cost of days of work lost due to migraine as calculated from the Migraine Work and Productivity Loss Questionnaire (MWPLQ)
- Score on the Migraine Disability Assessment Questionnaire (MIDAS) (0-21)
- 5) Scores on the emotional, restrictive and preventive portions of the Migraine-Specific Quality of Life questionnaire (MSQ)

The following comparisons will be made for the above measurements:

-Within Group A, compare all measurements before surgery to 1 year, 2 years and 2.5 years after surgery, using a t-test

-Within Group B, compare all measurements before start of injection protocol to 1 year, 2 years and 2.5 years after injection protocol, using a t-test

-Compare all measurements between Group A and Group B using a paired t-test analysis

e. Internal validity

The study avoids confounding by virtue of the matched-pair analysis. The study avoids recall bias by having the patients fill-out the questionnaires preoperatively and postoperatively, rather than having them retrospectively assess their improvement after surgery.

Blinding is very difficult in such a study. In order to avoid experimenter bias, all assessment will be made by the patients themselves, without influence by the experimenters.

The main threat to internal validity is the possible placebo effect inherent to migraine headache treatments. This may threaten the validity of the data on differences in clinical outcomes between the two groups. It will not threaten the validity of the data on financial cost

f. External validity

Because this is a multi-center trial that includes different patient populations treated by different clinicians, this study is generalizable to the general population of patients with migraines in the United States.

g. Data analysis

Group B will be selected by matching individual participants to members of Group A based on gender, age, migraine severity and migraine location.

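### Baseline is collected, but the protocol's paired t-test and the SAP's treatment main effect and same-visit comparisons do not adjust the surgery-versus-botulinum difference for it

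*SAP*

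**What the plan says.** **Baseline data.** Under Detailed study procedures, the protocol has patients "complete three questionnaires: the Migraine Work and Productivity Loss Questionnaire (MWPLQ"), MIDAS and MSQ at enrolment, and keep a headache diary for two months. The SAP lists baseline, 1, 2 and 2.5 years as the time points for the patient-reported outcomes.

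**Protocol test.** Measurements says: "Compare all measurements between Group A and Group B using a paired t-test analysis". Data analysis repeats this. Neither section names a covariate or says whether follow-up values or changes are compared.

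**SAP model.** Data Analysis says: "Linear mixed models with a random effect for patient were used to evaluate the changes in each of six outcomes between two different treatments over" [...]. The terms are treatment, time, treatment-by-time and a random patient effect, applied to ln(y+1) for six outcomes. P-values are reported for both main effects and the interaction, with Tukey adjustment of pairwise comparisons. No baseline covariate or pair term appears.

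**Group formation.** Group A is made up of patients who prefer surgery. Group B is matched to it on gender, five-year age band, five-point MIDAS band and trigger site.

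**The concern.** Objective 1 rests on the surgery-versus-botulinum comparison, with 50 patients planned per group. A patient's own baseline usually predicts follow-up, and here it costs nothing extra to use. A contrast that leaves it out carries avoidable error. Because treatment is chosen, such a contrast also passes any baseline difference between the groups into the estimated effect.

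Matching covers this only in part. MHI, MSQ and MWPLQ are not matched on their own baselines, and MIDAS is matched only within a band. The protocol's statement under Internal validity that matching removes confounding therefore does not settle the matter.

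**Working it through.** **1. Inputs from the protocol's sample-size section.** Botulinum patients "had an average improvement in their Migraine Headache Index of 87.5" percent; "patients undergoing surgery had an average improvement of 96.6" percent. The difference is 96.6 − 87.5 = 9.1 points. The section continues: "Assuming a standard deviation of 20%, an alpha error of 5%, and a power of 80" percent. The SAP adds: "Statistical significance was defined as two-sided alpha<0.05". Planned enrolment is 50 per group. Rho is in neither document; I assume 0.5, with a range of 0.3 to 0.7.

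**2. The plan's own figure.** The protocol's result is "30 patients in each group".
- Paired, n = (20 × (z_alpha + z_beta) / 9.1)²: 29.9 one-sided, 37.9 two-sided.
- Two-sample, twice that: 59.7 one-sided, 75.8 two-sided.

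So 30 is reproduced only as a one-sided paired test with 20 as the SD of pair differences. Under the SAP's two-sided 0.05 it is not reproduced. I therefore show paired and unpaired results.

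**3. What each contrast does with baseline.**
- *Paired t-test of measurements at a visit, or same-visit Tukey comparison:* no adjustment.
- *Treatment main effect:* if baseline is one of four time levels, it averages over baseline. A constant effect d at three follow-ups and zero at baseline gives 3d/4. If baseline is left out of the model, it is unadjusted.
- *Treatment-by-time:* a change contrast if baseline is a time level.

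**4. Relative variance at one visit** (common variance, equal expected baselines): follow-up only 1; change 2(1 − rho); baseline-adjusted 1 − rho².

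| rho | change | adjusted | cut vs follow-up only | cut vs change |
|---|---|---|---|---|
| 0.3 | 1.40 | 0.91 | 9% | 35% |
| 0.5 | 1.00 | 0.75 | 25% | 25% |
| 0.7 | 0.60 | 0.51 | 49% | 15% |

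For the main effect under equal correlations, the variance is (1 + 3rho)/4. Rescaled by (4/3)² to undo the dilution, it is 4(1 + 3rho)/9 = 0.84, 1.11, 1.38 at rho 0.3, 0.5, 0.7. The adjusted three-visit mean has (1 + 2rho)/3 − rho² = 0.44, 0.42, 0.31.

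**5. Power** (noncentral t, two-sided 0.05, difference 9.1, 50 per group). Unadjusted two-sample power with SD 20 is 61.5%.

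| rho | adjusted, 20 = SD of change: SD 20√((1+rho)/2) | adjusted, 20 = SD of follow-up: SD 20√(1−rho²) |
|---|---|---|
| 0.3 | 79.8% | 65.6% |
| 0.5 | 73.9% | 73.9% |
| 0.7 | 68.6% | 88.4% |

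The gains are 7 to 18 points against change and 4 to 27 against follow-up only. Paired, with 50 pairs and SD of differences 20, power goes from 88.4% to 95.4% at rho 0.5, about 7 points.

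**6. If the groups differ at baseline by g SDs.** Two cases: the gap persists, or it regresses to a follow-up gap of rho × g.

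| contrast | bias, stable gap | bias, regressing gap |
|---|---|---|
| follow-up only | g | rho × g |
| change | 0 | −(1 − rho)g |
| adjusted | (1 − rho)g | 0 |

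Against follow-up only, adjustment has the smaller bias in both columns. A gap inflates the adjusted variance by about 1 + g²/4. Even at g = 0.5 and rho = 0.3 it is 0.91 × 1.0625 = 0.97, still below 1. Simulation at rho 0.3, 0.5 and 0.7 with gaps of 0, 0.3 and 0.5 SD gave lower root mean squared error for adjustment than for follow-up only in every case.

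Against change there is no uniform winner. At rho 0.5 a stable 0.3 SD gap biases the adjusted result by 0.15 SD. With SD 20 that is 3.0 points, for a saving in SE of 4.00 − 3.46 = 0.54. Under a stable gap, mean squared errors break even at about g = √(2/50) = 0.2 SD. If the gap regresses, change is the biased contrast.

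**The case against.** The best defence is that a mixed model with baseline as a response is a standard choice. The SAP speaks of changes and lists baseline as a time point, so the natural reading is that the interaction uses baseline. This stands: a reader might infer that the plan ignores baseline altogether, and the documents do not support that.

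A second objection is that adjustment is not purely a gain in precision in a preference-based study. Change and adjusted contrasts can then answer different questions, and the documents do not say which pattern of baseline gap to expect. This also stands, and rules out simply replacing the interaction. It does not rescue the contrasts that leave baseline unadjusted, where step 6 favours adjustment in both cases.

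Third, a reader might take one figure, such as a 25% variance loss or 12 points of power, as the plan's loss. Those values need rho = 0.5, and the 12 points also need an unpaired two-sided test, whereas the protocol's test is paired. The inputs are percent improvement, already relative to baseline, and the SAP models ln(y+1). Matching on MIDAS should also leave less to gain for that outcome. All of this stands as to size, but does not change the direction.

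**Conclusion.** The concern holds for three contrasts: the protocol's paired t-test read as a comparison of follow-up values, the SAP's treatment main effect, and its same-visit comparisons. None adjusts for the patient's own baseline, and each is less precise and more exposed to baseline differences than the collected data require.

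The size cannot be fixed from the documents. The ranges in steps 4 and 5 rest on the assumed rho and equal expected baselines, and no power figure here is the power of the SAP model. The variance ratios carry over to the log scale only with rho measured there. MHI is not defined in either document; I take its baseline from the SAP's list of time points.

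For the treatment-by-time contrast, the documents support reporting an adjusted result beside it, and do not support calling either one correct by default.

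**What to change.** **In the SAP, for each of the six outcomes:**
- State whether baseline is in the response vector.
- Model ln(y+1) at 1, 2 and 2.5 years with treatment, time, treatment-by-time, the patient's baseline ln(y+1) and baseline-by-time, keeping the patient random effect.
- Report the adjusted surgery-minus-botulinum difference at each visit, in place of the treatment main effect and the unadjusted same-visit comparisons.
- Keep the written mixed model with baseline as a response, for the within-group before-after comparisons and the treatment-by-time change contrast. Report that contrast beside the adjusted result and discuss any disagreement.

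**For any matched-pair test that is kept:** regress the within-pair follow-up difference on the within-pair baseline difference and test the intercept.

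**Cost.** SAP wording and a few lines of SAS; no new data or patients. The adjusted model uses a few degrees of freedom and loses patients with no baseline value, as well as those with no follow-up value. It removes only part of a stable baseline gap, which is why the change contrast stays alongside it.

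### No planned analysis estimates whether surgery's benefit lasts better than botulinum toxin's after year 1, and the treatment-by-time interaction cannot stand in for it

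*SAP*

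**What the plan says.** Protocol, II. Objectives, item 1a hypothesises that "the reduction is greater and more sustainable than that seen with a botulinum toxin injection protocol". That is two claims, one about size and one about persistence. Neither document defines the second.

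The SAP, Data Analysis, says "Linear mixed models with a random effect for patient were used to evaluate the changes in each of six outcomes", with a treatment-by-time interaction. The visits are given as "each time point (baseline, 1 year, 2 years and 2.5 years". On inference it says "P-values for both the main and interaction effects of time and treatment were reported for each model", "Tukey's post hoc method was used to adjust for pairwise comparisons" and "Statistical significance was defined as two-sided alpha<0.05". It does not say which pairs the Tukey comparisons cover, or whether time is categorical. Raw means and SDs are to be shown by visit and treatment.

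The protocol (d. Measurements and g. Data analysis) plans within-group t-tests of each follow-up visit against the pre-treatment value, and a paired t-test between the groups.

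**The concern.** Durability is about what happens once the initial benefit has been obtained. Does the group difference hold, shrink or grow between 1 and 2.5 years? The natural null is that the change from 1 to 2.5 years is the same in both groups.

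The only planned test of differential change is the interaction. Its null is that the two profiles are parallel over all four visits, including the step from baseline to 1 year. A larger initial drop under surgery breaks that null whatever follows. With more than one degree of freedom, the test also carries no direction.

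The follow-up to 2.5 years makes the question answerable, but half of Objective 1a has no estimate or interval attached to it. An interaction P-value cited in support of both halves would be evidence for the first only.

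**Working it through.** **Inputs from the documents.** Four visits and two-sided alpha 0.05 (SAP, Data Analysis); 50 per group, and a planning difference of 96.6 − 87.5 = 9.1 points with SD 20, so 9.1/20 = 0.455 SD (Protocol, Sample size). The documents give no rejection rate or power for the interaction or for durability. The nearest stated figure is 30 per group for efficacy. It comes back as (20 × (1.645 + 0.842)/9.1)² = 29.9, a one-sided paired formula. That confirms 9.1 and 20 as the planning inputs; nothing else here depends on it.

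**Assumed, because the documents are silent.** Categorical time (3 df), complete data, independent arms, equal SD, a common within-patient correlation ρ (compound symmetry, as a random patient effect implies), and 0.455 SD carried over to the ln(outcome + 1) scale.

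**Interaction test.** Let d_t be the group difference at each visit, in SD units. The noncentrality is λ = (n/2) × Σ(d_t − mean d)² / (1 − ρ), with 3 and 3 × (2 × 50 − 2) = 294 df.

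*Constant advantage, d = (0, 0.455, 0.455, 0.455).* Durability is identical. The sum of squares is 0.75 × 0.455² = 0.1553, so λ = 25 × 0.1553/(1 − ρ) = 3.88/(1 − ρ).

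| ρ | λ | Interaction significant |
|---|---|---|
| 0 | 3.88 | 34% |
| 0.3 | 5.55 | 48% |
| 0.5 | 7.76 | 63% |
| 0.7 | 12.94 | 86% |

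A simulation of 20,000 runs gave 63.5% at ρ = 0.5, and 5.3% with no difference at any visit.

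*Opposite answers to the durability question, ρ = 0.5.* For a fade, d = (0, 0.8, 0.4, 0.2), the mean is 0.35 and the sum of squares is 0.1225 + 0.2025 + 0.0025 + 0.0225 = 0.35. Then λ = 25 × 0.35/0.5 = 17.5 and rejection is 95%. The growth (0, 0.2, 0.4, 0.8) has the same sum of squares, so the same λ and the same 95%.

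**Durability contrast.** C = (2.5 years − 1 year) in Surgery minus (2.5 years − 1 year) in Botox. In SD units its variance is 4(1 − ρ)/n. At ρ = 0.5 this is 4 × 0.5/50 = 0.04, so SE = 0.20.

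- Equal advantage at 1 and 2.5 years: C = 0, and the test rejects 5% of the time whatever the size of the advantage.
- Difference in durability of 0.5 SD: 0.5/0.20 = 2.5, power about 70%.
- Difference of 0.25 SD: 0.25/0.20 = 1.25, power about 24%.

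**Tukey and the protocol t-tests.** Each Tukey pair compares two cell means, while C combines four. If the pairs run over the treatment-by-time cells, they include Surgery 1 v 2.5 years, Botox 1 v 2.5 years, and the group difference at each visit. A significant decline in one arm and none in the other is a comparison of two P-values, not a test of C. The protocol's within-group tests all refer back to the pre-treatment value, and its between-group test names no change after year 1.

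**The case against.** **Rejection under a constant advantage is not an error.** A reader might infer from the table that the interaction test has a false-positive rate of 34% to 86%. It does not. With no difference at baseline and a difference afterwards, the profiles are not parallel, and rejecting is correct evidence for the first half of Objective 1a. The SAP nowhere says that the interaction is its test of durability. This stands: the percentages show only what the P-value would be worth if it were used that way.

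**Fading does not make rejection more likely.** A reader might set the 95% for the fade beside the 63% for a constant advantage and infer the opposite, but that fade starts from a larger year-1 effect. From the same start at ρ = 0.5, fading rejects less often: 57% for (0.5, 0.25, 0.125) against 72% for a constant 0.5 SD, and 95% for (0.8, 0.4, 0.2) against 99% for a constant 0.8 SD.

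**The planned output is not silent on durability.** Cell-wise Tukey comparisons and the means by visit would let a marked fade be seen. The protocol's claim could also be read as the reduction from baseline still being present at later visits with surgery still ahead, which the planned comparisons do address. This narrows the gap. It does not close it, because a claim that one treatment lasts better than another is comparative and needs the difference in change with its uncertainty.

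**The sizes rest on assumptions.** This also stands. A constant advantage of 0.2 SD at ρ = 0.5 gives 15%, and the model works on a log scale ("A constant of 1 was added to outcome values before applying natural log function") for which no effect size or correlation is given. Dropout and the matched pairs are ignored.

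**Conclusion.** The concern holds in a limited form. Durability is half of Objective 1a, and neither document defines it or plans an estimate of the between-group difference in change after year 1. The interaction is a valid test that the changes differ somewhere between baseline and 2.5 years, but it cannot distinguish a stable, fading or growing advantage. That mismatch follows from the hypotheses being tested and depends on no assumed number. The percentages are conditional on the assumptions listed in the working, and none of them is a figure from the documents.

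The documents do not support the stronger inference that durability is left entirely to the interaction test: Tukey comparisons and visit means would show part of the pattern. What is missing is one formal contrast.

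**What to change.** In the SAP:

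1. Define the durability claim as a smaller loss of benefit from 1 to 2.5 years under surgery.
2. From the same mixed model, estimate (2.5 years − 1 year) in Surgery minus (2.5 years − 1 year) in Botox for each outcome, with a 95% CI. State for each outcome which sign favours surgery.
3. Make the claim only if the CI excludes zero in surgery's favour, and do not cite the interaction P-value as evidence for it.
4. Name one outcome for this claim, for example MHI, or adjust over the six. Six unadjusted tests would give 1 − 0.95⁶, about a 26% chance of at least one false positive in either direction if they were independent.
5. The SAP is written in the past tense. If the analyses are already done, label the contrast post hoc.

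The cost is one ESTIMATE statement per outcome and a few sentences, with no new data. The downside is that the claim becomes harder to make. The 70% power at correlation 0.5 needs a 0.5 SD difference in durability, which exceeds the whole planned efficacy difference of 0.455 SD; at 0.25 SD power is about 24%. A non-significant contrast should therefore be reported through its interval, not as evidence that the two treatments last equally well.
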